|---------------------------|---------------------------|----------------------------|--|
| - up to 18 months: | every 9 weeks             | weeks after randomisation: | 9, 18, 27, 36, 45, 54, 63, 72, 81 (+/- 1 week) |
| - up to 2 years:   | every 12 weeks            | “                          | 93, 105 (+/- 1 week)                           |
| - years 3 and 4:   | every 6 months (26 weeks) | “                          | 131, 157, 183, 209 (+/- 1 week)                |
| - at 5 years:      |                           | “                          | 260 (+/- 1 week)                               |
- In case of clinical suspicion of distant metastases, immediate adequate diagnostic procedures including CT-scan, whole body PET-CT, bone scans and MRI (as appropriate) should be used.  
Early progression at 9 weeks: Patients with tumour volume increase documented by CT scan 9 weeks after randomisation, but without appearance of new lesions or rapid clinical deterioration should continue to be treated with IMP and clinically observed with a stringent imaging schedule 4 weeks later to determine whether there has been a decrease in the tumour size or disease stabilisation, or alternatively continued PD which would terminate the trial treatment.  
Patients who discontinue study treatment for reasons other than progressive disease: Restaging should be repeated at time of discontinuation, except if already performed within 6 weeks prior to the last dose of study treatment.
- 14 **Adverse events:** All adverse events that occur within 100 days of the last administered study medication or within 100 days after the last visit in the observation arm must be documented. Symptoms present at baseline and at randomisation will be recorded on the adverse event forms as well.
- 15 **Thoracic radiation** will be administered concurrently to chemotherapy and should preferentially start at the same time as the first chemotherapy cycle (e.g. day 1 of cycle 1), if the patient can be enrolled before chemotherapy start. Otherwise, radiotherapy should optimally start at day 1 of cycle 2, i.e. in treatment week 4. As a latest start of radiotherapy day 1 of cycle 3 is allowed, but should be exceptional.

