### **7.3. Inclusion criteria for randomisation**

- 7.3.1. Chemo-radiotherapy completed per protocol: 4 cycles of chemotherapy,  $\geq 85\%$  of PTV of thoracic radiotherapy, as well as completed, mandatory PCI
- 7.3.2. Non-PD after chemo-radiotherapy and PCI
- 7.3.3. ECOG performance status 0-2
- 7.3.4. Recovery of all adverse events to a Grade  $\leq 1$ , except for fatigue, appetite, oesophagitis and renal impairment (where  $\leq 2$  is allowed) and alopecia (any grade)
- 7.3.5. Women of childbearing potential, including women who had their last menstrual period in the last 2 years, must have a negative serum or urine pregnancy test within 7 days before randomisation.

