Experimental Arm / Observation Arm	
Experimental arm: within 7 days of the end of each consolidation cycle (every 3 weeks during 4 induction cycles and every 2 weeks during maintenance)
 
Observation Arm: within 7 days of each visit, which takes place at weeks 9 and 18 (+/- 3 days) after randomisation, and thereafter every 18 weeks (+/- 1 week) for 15 months after randomisation.

Adverse Events after Randomisation	
After randomisation: within 14 days after randomisation (to record ongoing events present at randomisation);
 
Experimental arm: within 7 days of end of each cycle of IMP treatment;
 
Observation arm: to be completed within 7 days of weeks 9 and 18 and every 18 weeks thereafter;
 
End of treatment: within 7 days after end-of-treatment visit
 
100 days period after last treatment / last visit in observation arm: within 14 days after follow-up visits

End of Treatment	Within 7 days after end of treatment visit (which is to take place as soon as possible after decision to end treatment/observation, but at the latest 30 days after the last dose of treatment/progression of disease)

CRF in ETOPdata	To be completed
Follow-up	
Follow-up before progression:  Within 14 days of clinical follow-up visits. In the first 18 months after randomisation these visits take place together with the CT scans (see above) and then at 3-monthly intervals until PD, for a maximum of 4.5 years after the enrolment of the last patient
 
Follow-up after progression:  <12 months post randomisation:  within 14 days of clinical follow-up visits (which take place at 3-monthly intervals from date of progression);  >12 months post randomisation:  within 14 days of clinical follow-up visits (which take place at 6-monthly intervals from date of progression) until death, for a maximum of 4.5 years after the enrolment of the last patient.
 
Follow-up on death:  To be completed within 14 days upon awareness of death.

Serious Adverse Event Initial Report	
Within 24h of awareness of SAE;  Must be submitted via ETOPDdata, submission via fax to ETOP safety office only in case of inavailability of ETOPdata.

Serious Adverse Event Follow-up Report	
Within 14 days of completion of initial report.  If event was not resolved after 14 days, submit an additional report again within 7 days of resolution of event.

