2.2.3 Exploratory endpoints

 TTD is defined as the time from the randomization to treatment discontinuation for any reason (including progression of disease, treatment toxicity, refusal, lost to follow-up and death). Censoring for TTD (patients on treatment or completed treatment), will occur at the last-follow-up date

 DoR is defined as the time from the documentation of tumour response (either partial or complete response) to disease progression or death. Censoring will occur at the last tumour assessment with response other than progression.

2.2.4 (Serious) Adverse Events

Adverse Events (AEs)

The main criterion for treatment tolerability is the occurrence of toxicities and adverse events. The severity and causality will be classified according to the NCI CTCAE version 4 (http://evs.nci.nih.gov/ftp1/CTCAE/About.html).

An adverse event is defined as any untoward medical occurrence that occurs from the day of enrolment in the Remote Data Entry (RDE) until 100 days after the final dose of IMP regardless of whether it is considered related to a medication. The relation of the adverse event with the administered trial treatment has to be indicated as: unrelated, unlikely, possible, probable or definite. In addition, any known untoward event that occurs subsequent to the adverse event reporting period that the investigator assesses as possibly related to the protocol treatment should be considered an adverse event.

Immune-related Adverse Events (irAEs)

The following adverse events are of special interest and must be documented after randomization in both treatment arms:

CTCAE Version 4.0 system organ class / preferred terms:

Nervous system disorders:

- Peripheral motor neuropathy
- Peripheral sensory neuropathy
- Meningismus
- Limbic Encephalitis
- Nervous system disorders Other, specify (Guillain-Barré, myasthenia gravis, aseptic or non-infectious meningitis)

Skin and subcutaneous tissue disorders:

- Stevens-Johnson syndrome
- Toxic epidermal necrolysis
- Bullous dermatitis
- Rash acneiform
- Rash maculo-papular
- Pruritus
- Skin and subcutaneous tissue disorders Other, specify

Gastrointestinal disorders:

- Colitis

- Diarrhea
- Colonic perforation
- Small intestinal perforation
- Gastric perforation
- Gastrointestinal disorders Other, specify

Hepatobiliary disorders:

- Hepatic failure
- Hepatitis viral
- Drug-induced liver injury (DILI)

Investigations:

- Alanine aminotransferase increased
- Aspartate aminotransferase increased

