4.7 Safety analysis

The safety analysis will be based on the safety cohort, i.e., all patients who have received at least 1 dose of IMP treatment (experimental arm) plus all patients randomized to observation arm, and will include the following:

- Overview of the number of patients who experienced an AE and/or a SAE, as well as
 the number of patients in the safety cohort who did not experience an event, along with
 respective percentages will be shown. This information will be presented overall and by
 treatment arm. Also, number of patients that entered the study with baseline symptoms
 will be reported.
- Number of AEs/SAEs will be presented overall and by treatment arm.
- Number of patients experiencing a specific number of AEs/SAEs, overall and by treatment arm.
- Distribution of (S)AEs by grade and CTCAE category, separately for the two treatment arms. Six columns, one for each grade and one for all (any) grades, will be shown (for each arm). An additional column (by arm) indicating which events were also SAEs will be also available. In this column, the frequency of the SAEs and the severity grade will be given. The percentages that will accompany the frequencies will be based on the respective frequency of an event over the total number of patients in the safety cohort and specific treatment arm. This table will include all (S)AEs irrespective of their relation to the trial treatment.
- Analogous table focusing only on the treatment related (S)AEs.
- Number and corresponding percentages of treatment related (S)AEs by grade, leading either to treatment discontinuation or death will be summarized for the two treatment arms.

- Maximum severity of adverse events (AE/SAE) for patients, overall and by treatment arm.

- Number of SAEs by center
- Detailed information of pulmonary AEs/SAEs of grade ≥3 will be summarized for the two treatment arms.
- The risk difference between the two treatment arms, along with corresponding 95%
 CIs for specific adverse evets (most frequent i.e. ≥15%, of any grade, or perhaps focus on grade ≥3, irrespective of relation to treatment or treatment-related).

Analogous (more concise) information will be reported for the adverse events during the chemo-radiotherapy phase of all enrolled patients who received at least one dose of chemo-radiotherapy (per-protocol safety cohort).

5 Technical details

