- o In all other cases, the patient will be censored at the date of randomization plus 1 day.

Reporting conventions

Regarding the estimates presented in the report, the following rules will be adopted:

- P-values ≥0.001 will be reported with three decimal places
- P-values >0.010 will be reported with two significant demical digits
- P-values less than 0.001 will be reported as "<0.001"
- Means, medians, 95% confidence limits (Cis), quantiles, and any other summary statistics, will be reported with one decimal digit
- Hazard ratios (HRs) and their 95% CI's will be reported to two decimals
- Estimated parameters, not on the same scale as raw observations (e.g. regression coefficients) will be reported to three significant figures.

Multiple recordings of an event for the same patient

There are some cases where a patient may experience the same event (AE/SAE) more than once. In such cases, the event will be counted only once for the calculation of the total number of events reported for the overall safety cohort.

Presentation of results

The results will be presented through tables and figures. A summary of the results will also accompany the main report. First, a short synopsis of the results will be presented through bullets, where only the most important findings will be shown. Following that, a more detailed description of the results will be provided, sectioned in the following order:

- Patient accrual and baseline characteristics
- Follow-up and Treatment administration

- Efficacy analysis
- Safety analysis

All tables and figures will be included in an appendix.

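### SAP 4.7 has no onset or worsening rule, so on a literal reading toxicity ongoing at randomisation counts in both arms and can dilute any-grade risk differences

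*SAP*

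**What the plan says.** **Recording.** Protocol Table 16 sets the first entry on the form for adverse events after randomisation as "within 14 days after randomisation (to record ongoing events present at randomisation". Footnote 14 of the trial schedule agrees: "Symptoms present at baseline and at randomisation will be recorded on the adverse event forms as well". Protocol 12.1 requires later changes in grade and resolution to be reported.

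**What can be ongoing.** Criterion 7.3.4 requires recovery to Grade 1 or less, "except for fatigue, appetite, oesophagitis and renal impairment", for which Grade 2 is allowed; alopecia may be of any grade. Randomisation falls on days 35 to 42 of chemotherapy cycle 4, and PCI may end as late as day 29 of that cycle.

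**Definition.** SAP 2.2.4 takes an adverse event as one that "occurs from the day of enrolment in the Remote Data Entry (RDE) until 100 days after the final dose of IMP". Neither randomisation nor first IMP dose starts the window.

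**Analysis.** SAP 4.7 tabulates events by arm and grade for the safety cohort: "This table will include all (S)AEs irrespective of their relation to the trial treatment". It adds a table restricted to treatment-related events, a summary of maximum severity, and risk differences for the most frequent events (at least 15%), "of any grade, or perhaps focus on grade ≥3, irrespective of relation to treatment or treatment-related". For baseline symptoms it plans only a count of patients. Events in the chemo-radiotherapy phase get a separate, more concise summary for all enrolled patients who received treatment. No rule covers an event that spans both phases.

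**The concern.** Safety and tolerability in both arms is a secondary objective (Protocol 5.2.2). The comparison should show what consolidation adds to observation. All randomised patients have just finished chemotherapy, thoracic radiotherapy and PCI, so low-grade residual toxicity is to be expected in both arms. If it counts as an event, a patient with carried-over Grade 1 fatigue is already a case in the any-grade column, and renewed or worse fatigue on nivolumab plus ipilimumab cannot make that patient a case again. Both arms' percentages rise together and the difference between them shrinks. The terms at risk are those common after chemo-radiotherapy, such as fatigue, appetite loss and oesophagitis. A residual term could also qualify for a risk difference through carry-over alone.

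**Working it through.** The plan states no figure to reproduce here, so the check is a simple model.

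**Inputs.** The documents give no carry-over rate, so p0 is assumed, equal in both arms under 1:1 allocation. qE and qO are the new-onset rates among patients without the term at randomisation. wE and wO are the rates of worsening among carriers.

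**Literal reading.** Arm rate = p0 + (1-p0)q, so the risk difference is RD = (1-p0)(qE-qO).

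**New or worsened events only.** Arm rate = (1-p0)q + p0·w, so RD = (1-p0)(qE-qO) + p0(wE-wO). The gain is p0(wE-wO).

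With qE-qO = 20 points:

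| p0 | Literal | Rule, wE-wO = 0 | Rule, wE-wO = 10 | Rule, wE-wO = 20 |
|---|---|---|---|---|
| 10% | 18 | 18 | 18 + 1 = 19 | 20 |
| 25% | 15 | 15 | 15 + 2.5 = 17.5 | 20 |
| 40% | 12 | 12 | 12 + 4 = 16 | 20 |

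**Precision.** Take one term with assumed new onset of 25% against 10%. Power (two-sided 0.05) serves only as a yardstick, since SAP 4.7 states no hypothesis test.

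| Per arm | p0 | Literal rates | RD (95% CI), points | Power |
|---|---|---|---|---|
| 130 | 0 | 25.0% v 10.0% | 15.0 (5.9 to 24.1) | 89% |
| 130 | 20% | 40.0% v 28.0% | 12.0 (0.6 to 23.4) | 53% |
| 130 | 40% | 55.0% v 46.0% | 9.0 (-3.1 to 21.1) | 31% |
| 75 | 0 | 25.0% v 10.0% | 15.0 (3.1 to 26.9) | 68% |
| 75 | 10% | 32.5% v 19.0% | 13.5 (-0.3 to 27.3) | 47% |

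130 per arm is the planned 260 divided by two. Accrual closed early (SAP 1.4.2) and the number randomised is not given, so 75 is an assumption.

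The rule also helps precision when it leaves the difference unchanged. At p0 = 40%, 130 per arm and no worsening among carriers, the rates are 0.6 × 25% = 15% and 0.6 × 10% = 6%. The difference is still 9.0 points. The standard error is √[(0.15×0.85 + 0.06×0.94)/130] = 0.0376, so the interval is 1.6 to 16.4 in place of -3.1 to 21.1.

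**Any event at all.** For illustration, take 76.6% in the experimental arm (the any-grade drug-related rate for this combination in Protocol 11.2.3) and an assumed 30% under observation. The literal difference is 46.6 points at p0 = 0, 28.0 at 40% and 18.6 (9.4 to 27.8) at 60%. It is diluted, but still clear.

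**The 15% threshold.** With no new events, p0 = 15% is enough to qualify. With 10% new onset, p0 + (1-p0)×0.10 ≥ 0.15 gives p0 ≥ 0.05/0.90 = 5.6%.

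**Grade ≥3.** Criterion 7.3.4 makes p0 about 0 here, so the factor (1-p0) is about 1.

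**The case against.** The strongest reply is that the case rests on silence. No sentence says ongoing events enter the arm comparison. The phases have separate forms, chemo-radiotherapy toxicity has its own summary, and patients with baseline symptoms are counted. This stands to the extent that the counting is a literal reading and not an express instruction. But the word all, applied to a form that holds these events under a window opening at enrolment, includes them.

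A reader might infer that carry-over masks the added toxicity of consolidation. The documents do not support that:

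- Carry-over is limited to Grade 1-2 apart from alopecia, and it raises both arms about equally.
- Carried-over Grade 1 diarrhoea that reaches Grade 3 still shows in the grade columns and in maximum severity.
- The net direction is not established. Adverse event forms are due every cycle in the experimental arm, but at weeks 9, 18 and then every 18 weeks under observation, which may push differences upward.
- Protocol 4.7 places radiation pneumonitis mostly 2-6 months after radiation. Much of it may start after randomisation, and an onset rule would not remove that.

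A reader might also lean on the duplicate rule in SAP 5, "In such cases, the event will be counted only once". That sentence concerns total event counts in the overall safety cohort and does not address carry-over or per-arm risk differences. The dilution does not need it, because a proportion of patients counts each patient once anyway.

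Finally, the treatment-related table would exclude carry-over if related meant related to IMP. The documents leave this open. Causality is judged against the administered trial treatment, and both Protocol section 10 and SAP 1.3 describe chemotherapy, radiotherapy and PCI under that title. The table helps but is not a sure safeguard.

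**Conclusion.** The concern holds as a gap in the SAP with a predictable effect. Read literally, the plan counts residual low-grade chemo-radiotherapy toxicity in both arms, which multiplies any-grade, all-cause risk differences by (1-p0). At assumed carry-over of 10% to 40%, a 20-point difference is tabulated as 18 to 12.

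It would be wrong to infer that an emergent-event rule restores the full 20 points. It adds p0(wE-wO), and reaches 20 only if carriers worsen with the same arm difference as others show in new onset.

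This rests on assumed p0, q and w, and on equal carry-over. The last is plausible but not strictly guaranteed, because the safety cohort drops experimental patients who received no IMP but keeps all observation patients. Grade ≥3 comparisons, and immune-related terms rare before randomisation, are largely unaffected. The change is still worth making, because any-grade risk differences are a named output and the definition should be fixed before the data are tabulated.

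**What to change.** In SAP 4.7:

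1. Base the between-arm any-grade tables, maximum-grade summaries and risk differences on events with onset after randomisation, or present at randomisation and worsening in grade afterwards.
2. Show events ongoing and unchanged since randomisation in a separate column.
3. State that treatment-related in the post-randomisation tables means related to IMP.

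The cost is SAP wording and one derived flag. Headline any-event percentages will be lower than a raw count. The grade changes needed are already reportable under Protocol 12.1. SAP 5 provides for imputing missing adverse event dates, which suggests that dates are collected, but the form's fields are not in the documents. The availability of onset dates should therefore be confirmed first.

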### 12.8. Reporting SAEs and protocol-specified significant events

Following the patient's written consent to participate in the study, all SAEs, whether related or not to study drug, must be collected, including those thought to be associated with protocol-specified procedures. All SAEs must be collected that occur within 100 days of the last administered study medication or within 100 days after the last visit in the observation arm.

Any SAE must be reported by submitting the completed SAE Initial Report eCRF in the RDE system within 24 hours of awareness.

DILI are to be reported by submitting the completed SAE Initial Report eCRF in the RDE system, even if they do not meet any of the seriousness criteria. Please submit the completed SAE Report eCRF (initial and follow-up) in the RDE system within 24 hours if the event is serious, or within 5 days, if the event is non serious, after awareness of the event. Indicate in "Description" section if "non-serious adverse event of special interest" yes or no

Submission of SAE is done via the electronic data capture system, or in case of unavailability, by sending the SAE form by fax to the ETOP Safety Office:

[contact]

Once the RDE system is available again, the SAE eCRF has to be completed and submitted by the site.

The SAE outcome must be reported within 14 days after initial reporting by online submitting the SAE Follow-up Report eCRF. In case the SAE is reported as ongoing after 14 days, the follow-up report has to be submitted again with the final outcome.

The ETOP Safety Office will forward each SAE to the trial chairs and notify principal investigators of any SADR meeting the criteria for expedited reporting (SUSAR) within the time-lines specified in GCP.

The local Ethics Committee must be informed by the principal investigator about local SAEs (if applicable by local law).

The ETOP Safety Office will inform Bristol-Myers Squibb (by e-mail to [[contact]](mailto:[contact])) of all SAEs – regardless of relatedness – and other appropriate persons (per either investigator or ETOP Safety Office review) within 24 hours of receipt.

The ETOP Safety Office will record the SAE and prepare a summary report of all SAEs received. Listings of SAEs will be prepared as required.

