#### b) Maintenance:

Nivolumab at a dose of 240 mg i.v. over a period of 30 minutes, once every 2 weeks (+/- 2 days, without dosing delay) for maximum 12 months from start of maintenance phase. The first dose of maintenance nivolumab will be administered 3 weeks after the last IMP doses of induction phase

Upon disease progression or completion of trial treatment, further therapy will be at the discretion of the treating physician.

16.1.4. **End of treatment:** an end of treatment visit will occur within 30 days following the last administered dose of trial treatment. For patients in the observation arm the end of treatment visit is to be scheduled within 30 days following PD or 15 months after randomisation. For patients who have not been randomised the end of treatment visit is to be scheduled within 30 days following PD or within 30 days following the last chemotherapy cycle.

16.1.5. **Follow-up period**

16.1.5.1. Before tumour progression: In the first 18 months after randomisation follow-up visits will occur together with the CT scans according to the schedule indicated in section 13.2, then every 12 (+/- 1) weeks until PD for a maximum of 4.5 years after the enrolment of the last patient.

16.1.5.2. After tumour progression: follow-up visits will occur every 12 weeks in the first year after randomisation starting from date of progression, then every 6 months up to 4.5 years after the enrolment of the last patient. This applies also to patients who have been enrolled but not randomised (see section 18.4).

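### The all-cause safety summaries in SAP 4.7 can count toxicity of anticancer therapy started after progression, because the collection window runs past the switch and no event is cut or flagged there

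*SAP*

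**What the plan says.** **What is tabulated.** SAP 4.7 describes the main table of events by grade and category thus: "This table will include all (S)AEs irrespective of their relation to the trial treatment". It adds a maximum-severity summary, a summary of grade ≥3 pulmonary events and risk differences for the most frequent terms. The scope of the risk differences is left open: "irrespective of relation to treatment or treatment-related". A further table is planned: "Analogous table focusing only on the treatment related (S)AEs".

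**How long events are collected.** Protocol section 2, footnote 14, requires events to be documented "within 100 days of the last administered study medication or within 100 days after the last visit in the observation arm". Protocol 12.8 applies the same limits to SAEs: "All SAEs must be collected that occur within 100 days of the last administered study medication", or after the last visit in the observation arm. Protocol Table 16 keeps the adverse event form due during this period. SAP 2.2.4 ends the period 100 days after the final IMP dose and gives no end for observation patients.

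**When the observation clock starts.** Protocol 16.1.4 places that arm's end-of-treatment visit "within 30 days following PD or 15 months after randomisation".

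**What may happen in the window.** Protocol 16.1.3: "Upon disease progression or completion of trial treatment, further therapy will be at the discretion of the treating physician". Further lines are documented after progression (Protocol 16.10) and described by arm (SAP 4.2). Neither document uses them to end, split or flag adverse event counts.

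**The concern.** Once a progressing patient starts another anticancer drug, its haematological, infectious or pulmonary toxicity enters the all-cause counts under the arm to which the patient belongs. Adjusting for length of observation does not remove such events, because a different drug causes them.

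The treatment-related table is a weak substitute. The observation arm receives no trial drug after randomisation and attribution is open-label, so that table has no meaningful comparator. The all-cause contrast is the main controlled safety comparison in the final analysis.

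The windows also differ by design. On IMP, dosing is every two to three weeks and the 100 days usually start before progression. In observation they can start up to 30 days after it. If the drug delays progression, or IMP is often stopped early, more observation than experimental patients would have second-line therapy inside the window, and the apparent excess toxicity of consolidation would shrink.

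**Working it through.** **Inputs from the documents**
- PFS medians of 13.1 and 22.8 months, HR 0.57, one-sided alpha 0.05, 80% power, 81 events (SAP 1.4.2 and 3).
- Windows as set out above.
- Stopping for treatment-related events on the combination: 11% in SCLC (Protocol 11.2.3) and 36.4% in melanoma (Protocol 11.3).
- Related grade 3–4 events on the combination: 34% and 55.0% (same sections).

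**Assumed, because the documents give no figure**
- Second-line uptake 50–80% of progressors, starting 14–42 days after PD.
- Probability t of a second-line grade ≥3 event inside the window: 20–60%.
- Background grade ≥3 risk b: 10–20%.
- Exponential PFS.

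**1. The plan's own figure.** Schoenfeld's formula with HR = 13.1/22.8 = 0.5746 gives 81 events, as stated. The rounded HR of 0.57 gives 79. The medians can be used as they stand.

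**2. Longest observation window after PD.** 30 + 100 = 130 days.

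**3. Share with a PFS event by 15 months**
- Observation: 1 − 0.5^(15/13.1) = 0.548.
- Experimental: 1 − 0.5^(15/22.8) = 0.366.

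Both are upper bounds for progression, because deaths count as PFS events.

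**4. Share with second-line therapy inside the window** (simulation, 1,000,000 patients per arm; each range runs from 50% to 80% uptake)

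| PFS | Early IMP stops | Observation | Experimental | Gap, points |
|---|---|---|---|---|
| Design medians | none | 30–48% | 20–32% | 10–16 |
| Design medians | 11% | 30–48% | 19–30% | 11–18 |
| Design medians | 36.4% | 30–48% | 15–24% | 15–24 |
| Equal (13.1 months) | none | 30–48% | 30–48% | 0.3–0.4 |
| Equal | 11% | 30–48% | 28–44% | 3–4 |
| Equal | 36.4% | 30–48% | 22–36% | 8–13 |

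Under the design medians, affected patients have on average 69–96 second-line days in the window in observation, against 60–62 in the experimental arm.

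**5. Effect on an overall grade ≥3 risk difference.** Let i be the IMP excess (0.34 or 0.55) and pO, pE the shares from step 4. Treat the sources of events as independent and count each patient once.
- True difference: (1 − b)·i, which is 0.8 × 0.34 = 0.27 to 0.9 × 0.55 = 0.50.
- Observed difference: (1 − b)·[(1 − pO·t) − (1 − i)(1 − pE·t)].
- Dilution: (1 − b)·t·[pO − (1 − i)·pE].

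Design medians:
- Smallest: 0.8 × 0.2 × (0.301 − 0.66 × 0.203) = 0.027.
- Largest: 0.9 × 0.6 × (0.481 − 0.45 × 0.238) = 0.202.
- Slightly lower share pairs (27% v 19%, 46% v 23%) give 0.023 to 0.193.

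The dilution is therefore about 2 to 20 points, and the observed difference stays positive in every case run. The lowest is 0.8 × 0.34 − 0.8 × 0.6 × (0.481 − 0.66 × 0.238) = 0.117.

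**6. Equal shares.** With pO = pE the formula leaves (1 − b)·t·p·i. This is a counting effect: a second-line event adds nothing in a patient who already has an event. It is not an imbalance between arms. The sign of the bias reverses only if pE exceeds pO/(1 − i).

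**The case against.** **Direction is not established.** This stands. The gap comes from the design HR and from early IMP stops. With equal PFS and no early stops it is 0.3–0.4 points, and if PFS is worse on IMP the affected shares could reverse.

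**Another bias runs the other way.** This also stands. Protocol 16.6 assesses observation patients at weeks 9 and 18 and then every 18 weeks, but IMP patients before each dose. Fewer observation-arm events will be captured. After progression, Protocol 16.10 schedules only survival and further lines, so second-line toxicity may be under-recorded as well.

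**The size is for a contrast that is not planned.** SAP 4.7 takes risk differences for individual frequent terms, and possibly only for related events. The figures above are for any grade ≥3 event. Bias in any single term depends on that term's own second-line risk, for which the documents give no figure.

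**There are other safeguards.** Protocol 11.4 and 18.5 plan an early 30-versus-30 pneumonitis evaluation and quarterly safety reviews, so the final table is not the only between-arm safety look. These do not repair the final summaries.

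**Counting everything in a fixed window is defensible, and a cut has its own bias.** True. Follow-up would be shortened most in the arm that progresses more, while percentages still use all patients as denominator. This argues against replacing the uncut tables, not against showing both.

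A reader might go further and infer that second-line toxicity could hide IMP harm. The documents do not support that: the treatment-related tables remain, and the calculation for overall grade ≥3 events shows dilution, never loss of the difference.

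**Conclusion.** The gap in the plan is a matter of text and does not rest on any assumption: the window runs past the switch, the main summaries are all-cause, and no event is separated at the start of new therapy. The maximum-grade and pulmonary summaries share the gap. The risk differences do so only if the all-cause option is used.

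The consequence is conditional. If PFS favours the experimental arm, or IMP is often stopped early, observation is affected more and the between-arm difference is diluted, by about 2 to 20 points for overall grade ≥3 events under the design medians and the assumed second-line figures. With equal PFS and no early stops the imbalance is near zero. The sparser observation visits pull the other way, so the net bias of the whole comparison is not fixed. It would be wrong to conclude that the planned tables must favour IMP. The point is worth correcting because the remedy is cheap and lets the reader see how much second-line toxicity matters.

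**What to change.** In SAP 2.2.4 and 4.7:
- State the collection window for both arms as in Protocol section 2, footnote 14, including the observation-arm end that SAP 2.2.4 omits.
- Flag each event as having onset before or after the start of the first subsequent anticancer therapy, taken from the further-lines record.
- Present the all-cause AE/SAE tables, the maximum-grade summary, the grade ≥3 pulmonary summary and the risk differences twice: uncut, and restricted to onset before that start. Apply the same rule in both arms.
- With the restricted version, show time at risk or exposure-adjusted rates, because follow-up then differs by arm.
- Keep later events judged IMP-related in the treatment-related table. Do not add events there merely because they are on the irAE list. That list includes pneumonitis, diarrhoea and transaminase increases, which are not specific to IMP, and adding them in one arm only would bring the contamination back.

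The cost is SAP wording, one derived flag and a few extra tables. It depends on start dates for further therapy being recorded, which the documents do not confirm. The rule in SAP section 5 that sets a date with missing day and month to 1 January could misplace a cut, so partial start dates should be listed.
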